11.0 BIOSTATISTICS

Overview. This exploratory study is divided into two phases. Phase I involves in-home interviews of 25 participants to understand the factors that affect participants' decision-making about UVR protection (sunscreen use, shade-seeking, use of protective clothing). Qualitative data analyses will be carried out in Phase I to generate an Ethnographic Decision-Tree Modeling (EDTM) tree as described in Section 4.2. For example, a participant may be most likely to use sunscreen when it is a sunny day and when he/she is outdoors, at the beach, or at an outdoor sporting event. The participant may also state that he/she uses sunscreen whenever together with a young child, even though it may not be a sunny day.

In Phase II, we plan to recruit a sample of 60 melanoma first degree relatives (FDRs) and use IVR technology so that they can record their daily sun protection behaviors and decision criteria. The IVR system will call participants twice daily at approximately 12:30 pm and 5 pm for a period of 14 days. The participant will use their telephone keypad to answer a series of questions on their UVR protection behaviors, which will be four dichotomous, self-reported outcomes: sunscreen use, shade-seeking, hat use, and protective clothing use). The assessment will also address factors that affect UVR protection behaviors. These decision factors are based on the qualitative data we collected in Phase I. For example, we will ask participants to report the presence or absence of environmental factors (e.g., weather conditions), convenience/situational factors (e.g., availability of sun protection items), and social-interpersonal (e.g., activities engaged in). Data collected through IVR will generally be analyzed by Generalized Estimating Equations (GEEs) to explore the decision factors that promote or hinder the probability of UVR protection behavior.

Specific Aim I: To generate models explaining decision-making about three UVR protection behaviors (sunscreen use, shade-seeking, use of protective clothing) in melanoma FDRs.

Aim I will involve the EDTM methodology described in Section 4.2. Audio-recorded narrative data will be coded and summarized into an EDTM tree.

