The general statistical paradigm for this Aim will be Generalized Estimating Equations (GEE) [83, 84] because of the repeated sampling of UVR protection behaviors and their predictors. Over a period of 14 days, each participant will generate a maximum of 28 assessments. Each assessment will yield 4 dichotomous outcome endpoints (sunscreen use, shade seeking, hat use and protective clothing). Additionally, each assessment will probe the decision factors, e.g., on environmental factors, convenience/situational factors, cognitive and social-interpersonal factors. For each outcome endpoint, we will fit a series of GEE models with a logit link. For example, we may fit the probability of sunscreen use as a function of weather (e.g., a dichotomous yes/no indicator of a sunny day). We will calculate the 95% confidence interval of the weather indicator on sunscreen use. The procedure will be repeated for other decision factors. We will use data visualization and graphs to summarize the 95% confidence intervals across decision factors, in the same exploratory procedures as outlined previously in O'Connor et al (2008).

Our exploratory GEEs approach is the most widely-used approach in the literature of intensive real-time data capture (aka Ecological Momentary Assessments, see Stone, 2009). Generally, these GEE models allow us to examine the extent to which each decision factor is associated with the health behaviors of interest. The repeated assessments will be clustered within persons. The working correlation structure will generally be fitted with an auto-regressive model because of the intensive daily assessments. The final number of covariates cannot be determined precisely at this time. However, care will be taken to minimize the number of confidence intervals to reduce concerns of multiple confidence intervals and to make the data more interpretable.

Power considerations.

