We estimated the statistical power of a GEE model on sunscreen use. The GEE model has a single covariate (e.g., a weather indicator). An extensive literature search did not find prior data on UVR protection behaviors. However, we believe that an odds ratio of 1.55 is plausible and is not overly optimistic. A hypothetical example helps explain this 1.55 difference. Suppose on a given day, 30 people report that it is sunny and the other 30 report that it is not sunny. Then an odds ratio of 1.55 means that we will be able to detect a difference between 70% (21 / 30) and 60% (18 / 30) sunscreen use across the two groups. Our power calculation showed that a sample size of 60 would be adequate in detecting this 70% vs. 60% difference.

Our actual statistical power estimation was based on a more sophisticated Monte Carlo simulation approach [86] as we consider study attrition and missed assessments. Formulaic solutions for GEE power calculations were deemed inadequate for the current study because they do not apply (e.g., the present study involves no randomization to study arms [87, 88]). Our Monte Carlo simulation showed that, with a sample size of 60 melanoma FDRs, accounting for clustering effect, respondent attrition and missed assessments,

we will have 78% power to detect a 1.55 OR in a GEE predictor at a two-sided Type-I error rate of 0.01 (0.01 Type-I error to provide some control over multiple GEE models).

To account for correlated longitudinal sunscreen use data nested within study participants, we assumed in the power calculation an ARI correlation pattern with a 0.50 co-occurrence probability between two consecutive days of sunscreen use. This 0.50 co-occurrence probability was based on the expected co-occurrences if, at any given day, 21 of 30 respondents use sunscreen. We can use a simple 2x2 table to demonstrate that, with the fixed marginals at 21 on either day, the expected sunscreen use on both days is 15 persons (a joint probability of $0.50 = 15/30$, below).

		Day 2	
		Use sunscreen (n=21)	No use (n=9)
Day 1	Use sunscreen (n=21)	15 (21*21)/30	6
	No use (n=9)	6	3

This 0.50 co-occurrence rate between consecutive days of 0.70 sunscreen use translates into a tetrachoric correlation coefficient of 0.082 (by the commonprob2sigma() function in the R package bindata). We thus used a rounded 0.10 tetrachoric correlation between two consecutive days in our simulation of an ARI correlation matrix.

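### Aim II is powered at a two-sided 0.01 to limit multiplicity, but its results are planned as 95% intervals, so that control is not applied

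*Combined protocol and SAP*

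**What the plan says.** Both statements stand in Section 11.0 and concern the same GEE models.

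The Aim II analysis text fits logit GEEs to four yes/no outcomes, one decision factor at a time: "We will calculate the 95% confidence interval of the weather indicator on sunscreen use. The procedure will be repeated for other decision factors". The display follows: "We will use data visualization and graphs to summarize the 95% confidence intervals across decision factors, in the same exploratory procedures". On multiplicity it says only that "care will be taken to minimize the number of confidence intervals to reduce concerns of multiple confidence intervals". It also concedes that "The final number of covariates cannot be determined precisely at this time".

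The power paragraphs describe the model that was sized: "The GEE model has a single covariate (e.g., a weather indicator"). They claim 78% power for an odds ratio of 1.55 with 60 participants at a "two-sided Type-I error rate of 0.01 (0.01 Type-I error to provide some control over multiple GEE models").

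Sections 3.0 and 9.0 add between-person and within-person forms of the belief predictors. The overview of Section 11.0 sets the frame: "This exploratory study is divided into two phases". No section applies 0.01, a 99% interval or any other formal adjustment to the Aim II results, and none declares a significance rule for them.

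**The concern.** The 0.01 was chosen for a stated purpose, which is to guard somewhat against false positives across many models. A Type-I level guards against anything only if the results are read at that level. A 95% interval corresponds to a two-sided 0.05, so the planned graphs are read at five times the error rate used for sizing. The 78% power also describes intervals that the plan does not produce.

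What is at stake is which decision factors appear to exclude an odds ratio of 1. The graphs are meant to show which factors help or hinder sun protection, and Section 3.0 expects the work to feed into interventions. The number of intervals is open: Section 7.0 lists 21 decision criteria, there are four outcomes, and the belief predictors come on top.

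**Working it through.** **Inputs.** All are from Section 11.0 unless noted: 60 participants; at most 28 assessments each; odds ratio 1.55, illustrated as 70% against 60% use with a 30:30 split; two-sided 0.01; power 78%; latent AR(1) correlation 0.10; 30% of assessments missing; attrition of 5% in week 1 and 5% of the remainder in week 2. Section 7.0 gives 21 decision criteria.

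**1. Does the 78% belong to 0.01?** The power was simulated again from these inputs with 28 assessments and robust standard errors. The documents do not say at what level the covariate varied or how dropout was timed, so several versions were run. The 0.10 was applied between successive assessments.

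| Covariate varies by | Working correlation | Runs | Power at 0.01 | Power at 0.05 |
|---|---|---|---|---|
| person | auto-regressive | 1000 | 78.7% | 91.3% |
| person | independence | 4000 | 78.8% | 93.0% |
| day | independence | 4000 | 79.7% | 92.7% |
| assessment | independence | 4000 | 82.1% | 93.8% |
| assessment | auto-regressive | 1000 | 83.0% | 93.3% |

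The plan says that "The working correlation structure will generally be fitted with an auto-regressive model", so the auto-regressive rows are closest to it. With 14 assessments, power is 43% to 47% at 0.01 and 67% to 69% at 0.05. Only 28 assessments at 0.01 comes close to 78%, so the stated figure is a 99%-interval figure.

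In null simulations with 28 assessments, rejection was 1.0% and 4.8% (auto-regressive) and 1.3% and 5.3% (independence). The nominal 1% and 5% are therefore reasonable below.

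**2. Standard error implied by the stated power.**
SE = ln(1.55) / (z for 0.995 + z for 0.78) = 0.4383 / (2.576 + 0.772) = 0.4383 / 3.348 = 0.131.

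**3. Power of the planned 95% intervals.**
Φ(3.348 − 1.960) = Φ(1.388) = 0.917, or about 92%. If 78% was rounded from 77.5% to 78.5%, the range is 91.5% to 92.0%.

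**4. Where an interval first excludes 1.**
- 95%: exp(1.960 × 0.1309) = 1.29
- 99%: exp(2.576 × 0.1309) = 1.40

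An estimate of 1.55 has a 95% interval of about 1.20 to 2.00 and a 99% interval of about 1.11 to 2.17. Estimates between 1.29 and 1.40 would be shown as excluding 1, although they miss the level used for sizing. If the true odds ratio is 1.55, the two levels disagree in about 92% − 78% = 14% of studies.

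**5. A less common factor (assumed 20% prevalence, not in the documents).**
SE is proportional to √[1/(p·p₁q₁) + 1/((1−p)·p₀q₀)], with p₀ = 0.60 and odds ratio 1.55. Relative to p = 0.5 the ratio at p = 0.2 is 1.274, so SE is about 0.167. The thresholds become 1.39 and 1.54. By this conversion power is 75% at 0.05 and 52% at 0.01. A direct simulation with auto-regressive working correlation (2000 runs) gave 79% and 58%, so the conversion is somewhat pessimistic here.

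**6. Chance exclusions.** Per 100 true-null intervals, 100 × 0.05 = 5 against 100 × 0.01 = 1 would exclude an odds ratio of 1. As an illustration, take all 4 × 21 = 84 outcome-factor pairs as null and independent:
- expected false exclusions: 84 × 0.05 = 4.2 against 84 × 0.01 = 0.84
- chance of at least one: 1 − 0.95^84 = 98.7% against 1 − 0.99^84 = 57.0%

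The plan fixes no number of intervals, so 84 shows scale only.

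**The case against.** The strongest reply is that the two levels need not conflict. The 0.01 appears only in the power paragraphs, and the analysis text is about estimation and display. Sizing at a strict level and then reporting conventional 95% intervals is coherent, because 78% at 0.01 is a lower bound on power at 0.05. The study and the GEEs are called exploratory, no significance rule is declared, only partial control is claimed, and multiplicity is acknowledged. One could also suppose that the models will be judged at 0.01, with 95% intervals as the display.

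Much of this stands. The sample size is safe, no confirmatory test fails, and unadjusted 95% intervals are ordinary in exploratory work. Even 99% intervals would leave a 57% chance of a false exclusion in the 84-interval illustration.

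What does not stand is the planning-only reading. The plan gives control over multiple models as its reason for 0.01, and control that exists only in the sizing controls nothing in the report. Nor does any text say that the models will be judged at 0.01. The analysis text's own worry about the number of intervals shows that they are expected to be read inferentially. The paper cited for the graphing procedure was not available, but the plan's own words specify 95%.

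**Conclusion.** The inconsistency is real. Section 11.0 sets 0.01 for multiplicity and then plans results at the 0.05 level, with nothing linking the two. The stated partial control is not delivered, and the 78% does not describe the planned intervals, for which power is about 92%.

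For the powered sunscreen model, the threshold for excluding 1 is an odds ratio of about 1.29 instead of 1.40. Each true-null interval has a 5% instead of a 1% chance of excluding 1. These figures rest on the stated 78% and a normal approximation, and other factors and outcomes will differ.

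The weight is minor to moderate. It should be fixed because the cure is cheap and a stated figure needs correcting or relabelling.

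**What to change.** Make the two parts of Section 11.0 use one level. Either option resolves the point.

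**Option A: keep the 0.01 and the 78%.** Change 95% to 99% in both sentences of the Aim II analysis text and make 99% intervals the single main display. Add: *A 99% interval that excludes an odds ratio of 1 matches the two-sided 0.01 level used for power; this is partial control and does not hold the family-wise error at 5%.*

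Cost: intervals are about 31% wider on the log scale (2.576 / 1.960 = 1.31). In the powered model a true odds ratio of 1.55 is missed about 22% of the time instead of 8%. For a factor at the assumed 20% prevalence, it is missed about 42% to 48% instead of 21% to 25% (simulation to conversion).

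**Option B: keep the 95% intervals.** State in the analysis text that they are descriptive and unadjusted for multiplicity. State in the power paragraphs that 0.01 was a planning level which the analysis does not apply. Restate power at 0.05 from a rerun of the sponsor's own simulation; about 92% is expected, but the exact value depends on settings that the documents do not give.

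Cost: one rerun of an existing simulation, and the claim of control is given up.

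A lighter variant keeps the 95% intervals and the 78% and writes in an explicit 0.01 rule for reading each factor. It needs no rerun, but the plotted bars would then show a different level from the rule.

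None of these changes the sample size or data collection.

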Health behavior theory may improve our understanding of the consistency of UVR protection. Witte's Extended Parallel Process Model [3] offers an account of the conditions under which illness threat may lead to health protective behavior. In the context of heightened illness threat (severity and susceptibility beliefs) and heightened beliefs that they can overcome the threat (self-efficacy and response-efficacy), people will act to do so via health protective behavior, or "danger control." In situations where threat is high but people don't believe they can manage it, behavioral avoidance, or "fear control" will result as people work to reduce their feelings of threat rather than their chances of becoming ill. Beliefs related to threat control include self-efficacy, or confidence that one can perform the behavior, and response-efficacy, or confidence that performing the behavior will protect against the health threat. Meta-analytic work examining this premise has found that pairing strong threat with high-self efficacy indeed maximizes behavior change [3]. In one of the only theories specifically addressing health behavior change maintenance, Rothman [50] has proposed and confirmed that satisfaction with the results of behavioral adoption - such as satisfaction with the results of smoking cessation or weight loss - determines whether individuals maintain health behavior over time [4, 5, 51].

We will examine these theory-based predictors - melanoma threat and efficacy, and satisfaction with UVR protection behavior - as between-subject and within-subject variables in this study. Accordingly, along with the most important decision factors, we will determine whether overall levels of these cognitive beliefs, or daily variations in these beliefs, are important in the maintenance of UVR protection over time in melanoma FDRs.

Study Significance. This is a measurement study aimed at understanding the discrete decision-making factors that dictate sun protection behavior on a daily basis. Given the clinical significance of even very few sunburn events, and the documented higher risk associated with some sun exposure contexts

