In addition to answering questions about their sun exposure and protection through the IVR phone keypad, at the end of each assessment participants will be asked by the IVR to record an audio narrative diary that will capture their own thoughts about their sun protection choices during that assessed time period (i.e., either the morning or afternoon on a given day in the 14-day assessment period). The IVR will direct participants with the following instruction after participants complete the assessment at both approximately 12:30 pm and approximately 5 pm. "Please now speak into your phone to describe in your own words your use of sun protection during the time period(s) you have just reported on." After the instruction to record the audio narrative, the IVR will inform the participant the time at which they will receive their next call. Theory-driven affective and cognitive predictors will include perceived risk for melanoma and efficacy (UVR protection self- and response-efficacy) based on Witte's Extended Parallel Process Model [3]. We will assess these predictors at each assessment point, twice daily for 14 days. We have elected not to include melanoma severity in the assessment given that it is generally not found to be predictive of UVR protective behaviors in melanoma FDRs [22, 25]. To measure perceived risk for melanoma we will use one established question that has been used in prior UVR protection studies with melanoma FDRs [22-26]: B) perceived absolute likelihood with verbal anchors (1 = no chance, 2 = unlikely, 3 = moderate chance, 4 = likely, 5 = certain to happen),

Efficacy beliefs [72] will be assessed through two questions assessing the extent to which the participant feels capable of UVR protection in general (self-efficacy; 1="Not at all capable," 2="somewhat incapable," "3=somewhat capable," "4="extremely capable") and the extent to which the participant believes that UVR protection strategies can prevent melanoma (response-efficacy; 1="Not at all effective," 2= "a little effective," 3= "moderately effective," 4= "extremely effective").

We will also assess satisfaction with UVR protection consistent with Rothman's theory of health behavior maintenance [50] via one question adapted to satisfaction with UVR protection based on Rothman's work on satisfaction with smoking cessation [4, 5]. Accordingly, we will ask "How satisfied are you with your

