decision to engage in sun protection behavior this morning (or) this afternoon?" (1="Not at all satisfied," 2 for "a little satisfied," 3 for "moderately satisfied," 4 for "extremely satisfied.")

Within a week of completing the final IVR assessment on day 14, the study staff will call the participants to complete a brief program satisfaction survey consisting of 17 items to address any barriers to using the IVR. Additionally, in accordance with prior ecological momentary assessment research, the IVR will ask participants to self-report the extent to which the IVR prompting acted as a cue-to-action in their two-week assessment period of sun protection behavior. It is expected to take about 5 minutes to complete.

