9.0 PRIMARY OUTCOMES

The following ultraviolet radiation protection (UVR) behaviors will be assessed as primary outcomes:

- Continuous sun avoidance and/or shade-seeking behavior
- Sunscreen use
- Use of UVR protective clothing
- Use of hats

Our first aim is to generate models explaining decision-making about three UVR protection behaviors (sunscreen use, shade-seeking, use of protective clothing) in melanoma FDRs. We will model daily decision-making processes for UVR protection through qualitative and quantitative research strategies. In Phase I, we will conduct in-home ethnographic interviews with 25 melanoma FDRs and generate a decision making model for each UVR protection behavior for each melanoma FDR, and subsequently construct a composite decision-making model for each of the UVR protection outcomes (i.e., sunscreen use, shade-seeking, and UVR protective clothing use) representing prominent decision making factors across all 25 FDRs interviewed. In Phase II we will establish the validity of the models via examination of daily decision-making about UVR protection using ecological momentary assessment via IVR (over 14 days in the summer/early fall, at approximately 12:30 pm and 5 pm daily) in 60 different melanoma FDRs from Phase I. As outlined in EDTM methodology, we will report on the level of success of the decision-making model in predicting uptake of each of the three UVR protection strategies.

Our second aim is to examine theory-driven affective and cognitive predictors of UVR protection maintenance (sunscreen use, shade-seeking, hat use, and use of UVR protective clothing) assessed in real time. We will examine the role of melanoma threat and efficacy beliefs in determining UVR protection maintenance drawn from Witte's Extended Parallel Processing Model [3], and will examine the role of satisfaction in UVR protection maintenance drawn from Rothman's theory of health behavior maintenance

[4-6]. We will examine both between-person and within-person changes in these predictors, as well as salient decision-making factors (Identified in Aim I), in predicting maintenance of sunscreen use, shade-seeking, hat use, and use of UVR protective clothing.

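### The promised within-person effects have no model in Section 11, and an AR(1) working correlation can shift the coefficients of predictors that react to earlier behaviour

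*Combined protocol and SAP*

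**What the plan says.** Section 11.0 (Specific Aim II) plans a series of logit GEEs for each of four yes/no behaviours, with repeated assessments clustered within person. On the correlation structure it says only: "The working correlation structure will generally be fitted with an auto-regressive model because of the intensive daily assessments". It gives no rule for using another structure, no sensitivity fit and no variance estimator. The stated purpose is that the models "allow us to examine the extent to which each decision factor is associated with the health behaviors of interest".

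Section 9.0 asks for more: "We will examine both between-person and within-person changes in these predictors". Section 11.0 contains no person-mean term, no deviation term and no lag structure that would deliver this.

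The theory predictors (perceived risk, self-efficacy, response-efficacy, satisfaction) vary over time. Section 7.0 says of the risk and efficacy items: "We will assess these predictors at each assessment point, twice daily for 14 days". The satisfaction item in Section 7.0 concerns the participant's "decision to engage in sun protection behavior this morning (or) this afternoon", so it is rated after, and about, the behaviour being modelled. Section 3.0 adds the theory that "satisfaction with the results of behavioral adoption" determines whether a behaviour is maintained.

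**The concern.** GEE with a non-independence working correlation estimates the association of Y_t with X_t consistently only if the predictor's values at other times add nothing: E[Y_t | X_1, ..., X_T] = E[Y_t | X_t]. If doing or not doing something at one call changes the predictor at the next, X_(t+1) carries information about Y_t and the condition fails.

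The documents describe such a loop for satisfaction: behaviour leads to satisfaction, which leads to further behaviour. For self-efficacy and having items to hand it is a reasonable inference. Behaviour cannot change the weather.

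Aim II is at stake. Its within-person coefficients could be weakened or pushed past the null by the weighting, and robust standard errors would not reveal it, because they correct the variance and not the coefficient.

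**Working it through.** **1. The plan's own figure.** Inputs from Section 11.0 (Power considerations): 60 participants, up to 28 assessments, OR 1.55, two-sided alpha 0.01, tetrachoric correlation 0.10, 30% missed assessments, 5% plus 5% attrition. Simulation gives 77.5% to 79.6% power under several readings (the simplest reading gives 81.5% to 83.7%), so the stated 78% is reproduced. That calculation says: "The GEE model has a single covariate (e.g., a weather indicator". The simulated covariate was likewise unaffected by behaviour, so the 78% says nothing about feedback.

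**2. Why the coefficient moves.** The estimating equation is Σ D_i′ V_i⁻¹ (Y_i − μ_i) = 0. Under AR(1) with equal spacing, V⁻¹ links neighbouring times with weight proportional to −ρ/(1 − ρ²). This adds terms of the form −ρ · X_(t+1) · (Y_t − μ_t).
- Positive feedback makes the expected product positive. For ρ > 0 the added term is then negative and the coefficient falls.
- Negative feedback reverses the sign.
- If ρ = 0, or there is no feedback, the term vanishes.

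**3. Size in the model as Section 11.0 describes it (no separation).** The target is the cross-sectional OR of Y_t on X_t. Feedback strength and persistence are assumed, because the documents give neither.
- Feedback OR 4, no residual correlation: 1.544 against 1.545, so no shift.
- Feedback OR 2 to 4, fitted ρ 0.05 to 0.07: −7% to −17% on the log OR. Examples: 1.58 becomes 1.53, 1.62 becomes 1.55, 1.68 becomes 1.53.
- Feedback OR 2 to 4, fitted ρ 0.17 to 0.30: −27% to −65% (1.78 becomes 1.50; 2.03 becomes 1.28). At 60 participants, coverage of the robust 95% interval was 0.89 down to 0.20, against 0.93 to 0.96 under independence.
- Feedback OR 0.5, ρ 0.23: +51% (1.30 becomes 1.49).
- Satisfaction-type predictor reacting to same-period behaviour, with or without earlier behaviour: −2% to −10%.

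The stated power implies SE = ln(1.55)/(2.576 + 0.772) = 0.438/3.348 = 0.131. Near the plan's correlation, ln(1.62/1.55) = 0.044 is 0.3 SE and ln(1.68/1.53) = 0.094 is 0.7 SE.

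**4. What the plan's correlation is worth.** The plan takes 21 × 21/30 = 14.7, the count expected if the two days were independent, and rounds it to 15. Then (15/30 − 0.49)/(0.7 × 0.3) = 0.048 on the binary scale. This matches the plan's tetrachoric 0.082, which was recomputed as 0.0817. Rounding up to 0.10 gives about 0.06. The value comes from rounding and is not evidence on persistence.

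**5. Size with person mean and deviation entered separately.** Model: logit P(Y_t = 1) = 0.6 + θX_t + b_i, with X_t more often high after use. Assumed: feedback OR 2 to 7, SD of b_i 0.7 to 1.8, 28 windows, 10,000 to 20,000 simulated persons.
- No feedback: the two structures agree to within 0.01.
- θ = 0: within-person OR about 0.8 to 0.95 under AR(1). Under independence it is about 0.96 to 0.99, falling to 0.93 in the most extreme settings.
- θ = 0.5, SD 1.8, feedback OR 4: 1.22 under AR(1) and 1.45 under independence, against 1.38 without feedback. On the log scale, (0.199 − 0.322)/0.322 = −38% and (0.372 − 0.322)/0.322 = +15%.

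**6. Independence without the separation.** Same model with θ = 0, SD 1.2, feedback OR 4: AR(1) gives 0.96 and independence gives 1.34. Here independence is further from the truth, because it mixes between-person and within-person association.

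**The case against.** The strongest reply is that bias needs a target, and Section 11.0 describes exploratory associations without setting one. Against the direct effect given the past, unseparated AR(1) was often the closer estimate. With no direct effect, feedback OR 4 and lagged-outcome persistence, AR(1) gave 1.01 while the cross-sectional OR was 1.35. This stands. It is why the missing within/between specification comes first and why changing the working correlation alone is not advised.

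Two further points stand in part. Feedback is inferred, and the plan's worked example is weather, where it cannot occur. The word generally also leaves room for other structures, but with no rule attached the choice would be made after the data are seen.

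A reader might infer that all Aim II coefficients are biased, that the 78% power is wrong, or that an independence structure yields a causal within-person effect. The documents support none of these. Environmental factors are not changed by behaviour, the power figure is reproduced for its own covariate, and independence leaves a residual bias. Nor does the plan rely on robust standard errors as a safeguard; it does not mention them.

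**Conclusion.** The point holds in a conditional form. Section 9.0 promises effects that the Section 11.0 models do not separate. For predictors that behaviour can change, the planned working correlation can distort those effects, usually downward under positive feedback. The shift is modest near the plan's assumed correlation (−7% to −17% on the log OR, under one standard error in the two cases worked) and larger with stronger persistence or person heterogeneity. The documents quantify neither of these, nor the strength of feedback, so every size here is a range over assumptions.

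For satisfaction, a separate limit matters at least as much. It is rated after the same-period decision, so its coefficient is an association whichever structure is used.

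**What to change.** In Section 11.0, for the theory predictors and any decision factor that behaviour can change (list them before analysis), specify:

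- **Model:** logit P(Y_it = 1) = β0 + β_B · x̄_i + β_W · (x_it − x̄_i), where x̄_i is the participant's mean over completed assessments. Report β_B and β_W separately.
- **Fit:** independence working correlation with participant-level robust standard errors.
- **Sensitivity:** the same model with AR(1), reporting any change in β_W.
- **Caveats:** a small residual bias remains, because the person mean includes later values that react to behaviour. Same-period satisfaction is to be read as an association only.

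Make the first two changes together, for the reason shown in step 6. AR(1) may stay for weather and similar factors.

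The cost is a short text change with no new data. The downside is a small loss of efficiency for predictors without feedback. In the power reproduction with a day-level covariate, independence gave 78.6% and AR(1) 79.6%.
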